### APPROVED BY THE YALE UNIVERSITY IRB 12/20/2022

Pain is minimized by local anesthesia. Infection is avoided by adequate cleansing of the skin prior to intravascular line insertion. After arterial catheter removal, bleeding is prevented by direct pressure applied to the site for a minimum of 15 minutes followed by a pressure dressing (coban) that should be kept clean and dry until evening. Subjects will have their hand and finger blood supply examined after arterial cannulation throughout the study, and again following catheter removal. Also, subjects will be asked to abstain from aspirin and other NSAIDs for 7-10 days prior to arterial line insertion and 7-10 days following arterial line removal. Subjects will be provided a 24-hour emergency physician contact number to call if they encounter pain, discoloration, numbness, tingling, coolness, hematoma, inflammation, or any other unusual symptoms in the wrist or hand, or fever, chills or drainage from the vascular puncture sites, following the procedure. All medical staff at the PET center (RNs and MDs) are ACLS-certified and immediately available for urgent or emergency responses. In such a case that a subject would require further evaluation or stabilization, 911 would be called and the subject would be sent to the Emergency Department for evaluation and treatment. A nurse will provide discharge instructions outlining general instructions in addition to post-arterial catheter precautions, problems to watch for, and procedures to follow should such problems occur.

To minimize the risks associated with radiation we will ensure that the radiation exposure in each subject does not exceed Federal guidelines. The dose of radiation will be submitted for approval to the Yale-New Haven Hospital Radiation Safety Committee (RSC) and also reviewed by the Yale University Radiation Safety Committee (YU-RSC). All scans will be done in the presence of medical supervision and trained nursing staff in an institution specifically designed to support imaging studies. In the event of serious medical complications, the Yale University PET scan facilities have immediate access to or consultation with specialized medical units at the Yale-New Haven Hospital. Preparation of radiopharmaceuticals and execution of PET scans will be performed by radiochemists, physicians, and technologists of the Department of Diagnostic Radiology, Yale University School of Medicine. These professionals are qualified by training and experience in the safe use and handling of radionuclides. Subjects will be asked about their previous radiation exposure, and those who have had research exposure within the past year will be excluded if their cumulative annual exposure (including the present study) exceeds FDA limits.

To minimize risks associated with MRI, each subject will fill out the Yale Magnetic Resonance Research Center MRI Safety Questionnaire before the study. Only subjects who fulfill the criteria by this questionnaire will be eligible for the study. In addition, subjects will remove all metal (watch, hair pins, jewelry) and change into scrubs immediately prior to the study and pass through the metal detector in the MRRC before entering the MRI room. If the subject has any metallic prostheses/implants they will be excluded from the study. If a subject becomes anxious during the scan they can request that the MRI scan be stopped.

To minimize risks associated with pregnancy and breastfeeding we will not enroll women who are pregnant or breast-feeding.

To minimize risks associated with LPS administration we are administering a dose (1 ng/kg) that is 1/4 of the maximum dose (4 ng/kg) that can safely be used in human subjects research. Because we will enroll only physically healthy subjects under the age of 55 who have no cardiovascular problems and no history of vasovagal syncope, we do not expect that any subject will experience a serious adverse event. Subjects will be screened for a history of fainting or vasovagal syncope, and will be adequately hydrated prior to and during LPS administration. These measures are used to reduce the already very low odds of cardiovascular adverse events

12. Data and Safety Monitoring Plan: Include an appropriate Data and Safety Monitoring Plan (DSMP) based on the investigator's risk assessment stated below. (Note: the HIC will make the final determination of the risk to subjects.)

Page 22 of 45

- a. What is the investigator's assessment of the overall risk level for subjects participating in this study? The investigator views this as overall moderate risk for participation.
- b. If children are involved, what is the investigator's assessment of the overall risk level for the children participating in this study? No children will be enrolled in to this study.
- c. Include an appropriate Data and Safety Monitoring Plan. Examples of DSMPs are available here http://your.yale.edu/policies-procedures/forms/420-fr-01-data-and-safety-monitoring-plans-templates for
  - i. Minimal risk
  - ii. Greater than minimal

## DATA SAFETY MONITORING PLAN

Although this study qualifies as clinical research, it does not meet NIH criteria for Phase III clinical trial research. Nonetheless, this study will be monitored every 6 months by a Data Safety Monitoring Board (DSMB). Adequate surveillance and protections will be put in place to discover adverse events promptly and keep their effects to a minimum. There is an established DSMB at the Yale PET Center that meets every 6 months.

Expected and Unexpected Adverse Events will be recorded according to PET Center and NIH guidelines. Should an unexpected or serious AE occur, the PI will be notified immediately and appropriate report forms will be completed. AE's will be captured either in paper form or through digital RedCap forms.

## Attribution of Adverse Events.

We will use the Yale University School of Medicine – Human Investigation Committee recommended guidelines for assessing attribution adverse events.

### Attribution of Risk Categories:

Definite:	Adverse event(s) will clearly be related to investigational agent(s) or other intervention
Probable:	Adverse event(s) will likely be related to investigational agent(s)
Possible:	Adverse event(s) may be related to investigational agent(s)
Unlikely:	Adverse event(s) will doubtfully be related to investigational agent(s)
Unrelated:	Adverse event(s) will clearly not be related to the investigational agents(s)

### Plans for Grading Adverse Event.

For grading the severity of adverse events noted during the study we will adopt a general scheme from FDA publication *Guidance for Industry: Toxicity Grading Scale for Healthy Adult and Adolescent Volunteers Enrolled in Preventive Vaccine Clinical Trials (FDA, Center for Biologics Evaluation and Research, September 2007):* 

### Grades of Risk:

- 0 No adverse event or within normal limits
- 1 Mild adverse event: Does not interfere with activity
- 2 Moderate adverse event: Some interference with activity not requiring medical intervention
- 3 Severe adverse event: Prevents daily activity and requires medical intervention
- 4 Potentially Life-threatening or disabling adverse event: Results in an ER visit or hospitalization

Page 23 of 45

### 5 Fatal adverse event

Mild (Grade 1)	Moderate (Grade 2)		Potentially Life Threatening (Grade 4)
No interference with activity	Some interference with activity not requiring medical intervention	Prevents daily activity and requires medical intervention	ER visit or hospitalization

# 1- For most of the anticipated adverse effects we will use this guidance and parameters set:

*For arterial cannulation:* 

	Mild (Grade 1)	Moderate (Grade 2)	Severe (Grade 3)	Potentially Life Threatening (Grade 4)
Pain	Does not interfere with activity	Repeated use of non- narcotic pain reliever > 48hours or interferes with activity	Required use of narcotic pain reliever or prevents daily activity	Emergency room (ER) visit or hospitalization
Tenderness	Mild discomfort to touch	Discomfort with movement	Significant discomfort at rest	ER visit or hospitalization
Erythema/Redness *	2.5 - 5 cm	5.1 - 10 cm	> 10 cm	Necrosis or exfoliative dermatitis
Induration/Swelling **		5.1 - 10 cm or interferes with activity	> 10 cm or prevents daily activity	Necrosis

\* In addition to grading the measured local reaction at the greatest single diameter, the measurement should be recorded as a continuous variable.

\*\* Induration/Swelling should be evaluated and graded using the functional scale as well as the actual measurement.

# For vital signs:

Vital Signs *	Mild (Grade 1)	Moderate (Grade 2)	Severe (Grade 3)	Potentially Life Threatening (Grade 4)
Fever (°C) ** (°F) *	38.0 – 38.4 100.4 – 101.1	38.5 – 38.9 101.2 – 102.0	39.0 – 40 102.1 – 104	> 40 > 104
Tachycardia - beats per minute	Increased by >30% baseline beats per minute and then	Increased by 40% over baseline and then resolving over 15-30	Increase of >40% over baseline for greater than 30	HR >200 for >2 min, ER visit, or hospitalization

	resolving over 15- 30 Minutes	minutes	minutes	
Bradycardia - beats per minute***	Decreased by >30% baseline beats per minute and then resolving over 15- 30 minutes	Decreased by 40% over baseline and then resolving over 15- 30 minutes	Decreased of >40% over baseline for greater than 30 minutes	ER visit or hospitalization
Hypotension (systolic) – mm Hg	85 – 89 resolving in less than 5 minutes	80 – 84 resolving in less than 5 minutes	< 80 not resolving after 5 minutes	ER visit or hospitalization for hypotensive shock

\* Subject should be at rest for all vital sign measurements.

\*\* Oral temperature; no recent hot or cold beverages or smoking.

\*\*\* When resting heart rate is between 60 - 100 beats per minute. Use clinical judgement when characterizing bradycardia among some healthy subject populations, for example, conditioned athletes.

*For systemic symptoms:* 

Systemic (General)	Mild (Grade 1)	Moderate (Grade 2)	Severe (Grade 3)	Potentially Life Threatening (Grade 4)
Nausea/vomiting	No interference with activity or 1 - 2 episodes/24 hours	Some interference with activity or > 2 episodes/24 hours	Prevents daily activity	ER visit or hospitalization for hypotensive shock
Diarrhea	2 - 3 loose stools in 24 hours	4 - 5 stools in 24 hours	6 or more watery stools in 24 hours or requires outpatient IV hydration	ER visit or hospitalization
Headache	No interference with activity	Repeated use of non- narcotic pain reliever > 24 hours or some interference with activity	Prevents daily activity; required prescription of narcotic pain reliever	ER visit or hospitalization
Fatigue	No interference with activity	Some interference with activity	Prevents daily activity	ER visit or hospitalization

Serum for Screening *	Mild (Grade 1)	Moderate (Grade 2)		Potentially Life Threatening (Grade 4)**
Sodium – Hyponatremia mEq/L	132 – 134	130 – 131	125 – 129	< 125
Sodium – Hypernatremia mEq/L	144 - 145	146 – 147	148 – 150	> 150
Potassium – Hyperkalemia mEq/L	5.1 – 5.2	5.3 – 5.4	5.5 – 5.6	> 5.6

# Page 25 of 45

3.5 - 3.6	3.3 - 3.4	3.1 - 3.2	< 3.1
65 – 69	55 – 64	45 – 54	< 45
100 – 110 110 – 125	111 – 140 126 – 200	>140 >200	Insulin requirements or hyperosmolar coma
23-26	27 – 31	> 31	Requires dialysis
1.5 – 1.7	1.8 - 2.0	2.1 – 2.5	> 2.5 or requires dialysis
8.0 - 8.4	7.5 – 7.9	7.0 - 7.4	< 7.0
10.5 - 11.0	11.1 – 11.5	11.6 - 12.0	> 12.0
2.8 - 3.1	2.5 – 2.7	< 2.5	
1.1 – 2.5 x ULN	2.6 – 5.0 x ULN	5.1 – 10 x ULN	> 10 x ULN
1.1 – 1.25 x ULN	1.26 – 1.5 x ULN	1.51 – 1.75 x ULN	> 1.75 x ULN
1.1 – 1.5 x ULN	1.6 – 2.0 x ULN	2.0 – 3.0 x ULN	> 3.0 x ULN
1.1 x ULN	1.2-1.3 x ULN	1.4 – 1.9 x ULN	Greater than 2 if accompanied by >60% neutrophils of immature white cells
10-13.2 g/dl	8-10 g/dl	6.5-8 g/dl	<6.5 g/dl
100000 - 140000	70000-100000	50000 -70000	< 50000
	65 – 69 100 – 110 110 – 125 23-26 1.5 – 1.7 8.0 – 8.4 10.5 – 11.0 2.8 – 3.1 1.1 – 2.5 x ULN 1.1 – 1.25 x ULN 1.1 – 1.5 x ULN 1.1 x ULN 10-13.2 g/dl 100000 -	65 - 69       55 - 64         100 - 110       111 - 140         110 - 125       111 - 140         23-26       27 - 31         1.5 - 1.7       1.8 - 2.0         8.0 - 8.4       7.5 - 7.9         10.5 - 11.0       11.1 - 11.5         2.8 - 3.1       2.5 - 2.7         1.1 - 2.5 x ULN       2.6 - 5.0 x ULN         1.1 - 1.25 x       ULN         1.1 - 1.5 x ULN       1.26 - 1.5 x         1.1 - 1.5 x ULN       1.6 - 2.0 x ULN         1.1 - 1.5 x ULN       1.6 - 2.0 x ULN         1.1 x ULN       1.2 - 1.3 x ULN         10-13.2 g/dl       8-10 g/dl	65 - 69         55 - 64         45 - 54           100 - 110 110 - 125         111 - 140 126 - 200         >140 >200           23-26         27 - 31         >31           1.5 - 1.7         1.8 - 2.0         2.1 - 2.5           8.0 - 8.4         7.5 - 7.9         7.0 - 7.4           10.5 - 11.0         11.1 - 11.5         11.6 - 12.0           2.8 - 3.1         2.5 - 2.7         < 2.5

\*collected for screening purposes and subjects with grade 3 or higher ranges will not be considered for the study.

**\*\***grade 3 and below will not be considered reportable events.

# **STUDY STOPPING CRITERIA**

- a. >1 SAE at least possibly related to endotoxin administration
- b. >2 Grade 3 (severe) adverse events at least possibly related to endotoxin administration, based on appropriate grading scale (e.g., Toxicity Grading Scale for Healthy Adult and Adolescent Volunteers Enrolled in Preventive Vaccine Clinical Trials)

### Plans for Reporting Serious Anticipated and Unanticipated Adverse Events.

Serious anticipated adverse events occurring with a greater frequency than expected, and unanticipated adverse events that are possibly, probably, or definitely related to study procedures will be reported.

All SAEs will result in the completion of an SAE Form and a verbal report within one hour to the corresponding Principal Investigator ([name]). Within 24 hours, the following additional individuals will be informed: 1) the Co-PI and all Co-investigators; 2) the HIC; 3) the DSMB; 4) and NIMH. The Principal Investigator ([name].) will assume full responsibility for reporting serious adverse events. All of these individuals will receive a copy of the SAE Form at which point a decision will be made whether to convene a meeting of the DSMB. The DSMB and principal investigator will evaluate the adverse event and determine whether the adverse event affects the Risk/Benefit ratio of the study and whether modifications to the protocol (at Risks to Participants, or in Procedures) or consent form (at Risks and Inconveniences) are required.

The procedures for SAE reporting include written documentation using the clinical notes related to the adverse event and specific forms detailing the event with a sign-off by all appropriate supervisory personnel. Communication of recommendations and decisions from all parties (DSMB, Yale Human Investigations Committee) are made back to the investigator in a timely manner. We will report all protocol amendments or changes in the informed consent form to NIMH as well as any temporary or permanent suspension of patient accrual.

For Data and Safety Monitoring Plan templates, see http://www.yale.edu/hrpp/forms-templates/biomedical.html

- d. For multi-site studies for which the Yale PI serves as the lead investigator:
  - i. How will adverse events and unanticipated problems involving risks to subjects or others be reported, reviewed and managed? *Write here*
  - ii. What provisions are in place for management of interim results? Write here
  - iii. What will the multi-site process be for protocol modifications? Write here

**Study Hold Criteria:** The following is criteria that will be used to halt enrollment or further participation of enrolled subjects pending safety review based on: the number of adverse events considered possibly probably or definitely related to endotoxin administration.  $\geq 2$  grade 3 adverse events, > 1 grade 4 clinical or laboratory adverse event, or 1 grade 5 adverse event [

13. **Statistical Considerations:** Describe the statistical analyses that support the study design. Frequency distributions and descriptive statistics for all variables will be computed prior to conducting analyses. Should Shapiro-Wilk normality tests indicate non-normality for any continuous variable, we will compute necessary

# Page 27 of 45

data transformations (e.g., logarithmic base 10) prior to conducting analyses. Preliminary data revealed large (i.e., r's>.80) magnitude correlations among [C]PBR28  $V_{T}$  values in all of the brain regions assessed. Thus, we will conduct a principal components analysis with oblique (promax) rotation of [C]PBR28  $V_{T}$  values in all brain regions assessed to calculate a global composite measure of [C]PBR28  $V_{T}$  values.

A univariate ANCOVA will be used to compare global [C]PBR28  $V_{T}$  values between trauma-exposed controls and individuals with PTSD. Group (Control vs. PTSD) and rs6971 genotype on the TSPO gene will be entered as fixed factors(102), variables that differ between Control and PTSD groups as additional fixed factors (categorical variables *such as major depressive disorder*) or covariates (continuous variables *such as time since index trauma*), and global [C]PBR28  $V_{T}$  values as the dependent variable. A post-hoc multivariate ANCOVA will be conducted with the same independent variables and [C]PBR28  $V_{T}$  values in individual brain regions entered as dependent variables;  $\alpha$  will be set to 0.005 (0.05/10 brain regions) in this analysis to control for Type I error. To evaluate the relation between continuously distributed global [C]PBR28  $V_{T}$  values and measures of post-traumatic threat and loss symptoms, and neurocognitive functioning, we will conduct a linear regression model using Mplus version 7.31(124). In this analysis, global [C]PBR28  $V_{T}$  values will be modeled as the independent variable, and continuously-distributed scores on objective endophenotypic measures of threat and loss symptoms, and neurocognitive functioning, and clinician interview-based measures of threat and loss symptoms will be modeled as dependent variables. Should correlation analyses reveal large magnitude associations (i.e.,  $r \ge 0.70$ ) among variables will be modeled and analyzed as latent variables.

Linear mixed-effects models will be used to compare LPS-induced changes in [C]PBR28  $V_T$  values in the Trauma Control and PTSD groups. Group (Control vs. PTSD) and rs6971 polymorphism in the TSPO gene will be entered as fixed factors, subject as a random effect, pre-LPS global [C]PBR28  $V_T$  values as a covariate, and post-LPS global [C]PBR28  $V_T$  values as the dependent variable; variables that differ between Trauma Control and PTSD groups will be entered as additional fixed factors (categorical variables) or covariates (continuous variables). An ANCOVA with the rs6971 polymorphism in the TSPO gene and other variables that differ by PTSD status entered as covariates will be conducted to compare %change in [C]PBR28  $V_T$  values in the PTSD vs. Trauma Control group. Post-hoc analyses adjusted for multiple comparisons ( $\alpha$ =0.005; 0.05/10 brain regions) will be conducted to evaluate LPS-induced changes in [C]PBR28  $V_T$  values in individual brain regions in these two groups. Interrelationships among changes in outcome measures will be evaluated in the full sample and by PTSD group status using parallel process analyses in Mplus version 7.31.

Partial correlations adjusted for the rs6971 polymorphism will be conducted to examine associations between baseline and LPS-induced measures of global [C]PBR28  $V_T$  values, peripheral inflammatory markers, and endophenotypic and phenotypic measures of threat, loss, and neurocognitive function. Associated peripheral inflammatory markers will then be entered into a bias-corrected bootstrap test of mediation to evaluate whether global [C]PBR28  $V_T$  values mediate the relation between peripheral inflammatory markers, and measures of threat and loss symptoms, and neurocognitive function. A parallel set of tests of mediation will be conducted to examine whether LPS-induced increases in activated microglia mediate the relation between LPS-induced increases in peripheral inflammatory markers and the measures of threat and loss symptoms, and neurocognitive function. In this analysis, LPS-induced changes in peripheral inflammatory markers will be modeled as the independent variable, percent change in global [C]PBR28  $V_T$  values as the mediator variable, and LPS-induced changes in threat and loss symptoms and neurocognitive function as dependent variables. These tests employ a non-parametric bootstrapping procedure (10,000 samples) to generate estimates of direct and indirect effects, and confidence intervals(125-127). SECTION II: RESEARCH INVOLVING DRUGS, BIOLOGICS, RADIOTRACERS, PLACEBOS AND DEVICES

If this section (or one of its parts, A or B) is not applicable, check off N/A and delete the rest of the section.

[figure not shown]

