## d) Higher levels of activated microglia are associated with

**neurocognitive dysfunction**. Preliminary data (n=23) were analyzed to evaluate the relation between global [C]PBR28 *V*T values and performance on a comprehensive neurocognitive test battery developed by Cogstate (www.cogstate.com), which assesses processing speed, visual attention, verbal and visual learning and memory, visual working memory, and spatial problem-solving(104, 105). On average, this sample was 29.7 years old (SD=7.3, range=19-44), predominantly male (65.2%), ethnically diverse (43.5% African American, 30.4% Caucasian, 21.7% Hispanic, 4.3% Hispanic), and comprised of n=13 [56.5%] healthy controls, n=7 [30.4%] individuals with alcohol dependence and 3 [13.1%] with PTSD. Partial correlations adjusted for the rs6971 polymorphism on the TSPO gene and psychiatric disorder revealed that higher global [C]PBR28 *V*T values were associated with significantly worse performance on measures of learning and memory (r= -0.47, p=0.021), and working memory (r= -0.39, p=0.034). These results suggest that higher levels of activated microglia are associated with decrements in learning and memory, as well as working memory. In Aim 1, we will build on these preliminary results to determine how baseline levels of activated microglia contribute to neurocognitive dysfunction in PTSD.

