### **Sample Size Calculation**

Power calculations were conducted by a statistician and Co-I, [name]. Preliminary data from 6 individuals with PTSD and 8 trauma-exposed controls revealed robustly higher [C]PBR28 VT values globally (21.5% higher; d=1.02) and regionally (17.3-30.1% higher; d's=0.83-1.15) in PTSD vs. controls.}} Assuming a two-sided analysis of covariance (ANCOVA) with  $\alpha$ =0.05, recruitment of 40 trauma-exposed controls and 40 individuals with PTSD (quartiles 3-4) will provide greater than 94.2% statistical power to detect effect sizes as small as d=0.80. This translates into minimum detectable differences between controls and individuals with PTSD of 15.0%. To examine relations between continuous measures of global and regional [11C]PBR28 V1 values, and measures of post-traumatic threat and loss symptoms, and neurocognitive functioning, preliminary data from 5 individuals with moderate-or-greater severity of MDD symptoms revealed a strong association between global [11C]PBR28  $V_{T}$  values and severity of loss/anhedonic symptoms (r=0.82). Further, preliminary data from 23 individuals revealed that global [ $^{11}$ C]PBR28 VT values correlated significantly with measures of learning and memory (r= -0.47) and working memory (r= -0.39). Thus, assuming a two-sided linear multiple regression model with  $\alpha$ =0.01 (0.05/5 dependent variables: dot probe and PRT scores, CAPS-5-assessed threat and loss symptoms, global cognition) and conservative overall model effect size (R^2) of .25, and up to 10 predictors, an n of 80 will provide 99.2% statistical power to detect this magnitude effect. Our previous study in 8 healthy controls revealed robust LPS-induced increases in [ $^{11}$ C]PBR28 VT values ranging in magnitude from 31% to 63%(13). We have preliminary data indicating an overall 8.8% difference (d=0.38)in global [C]PBR28 VT values between 2 individuals with PTSD and 2 matched trauma-exposed controls. Thus, assuming a minimum 8.0% differential increase in LPS-induced  $[^{11}C]PBR28 V_T$  values in the PTSD group relative to trauma-exposed controls(16),  $\alpha$ =0.05, correlation among repeated measures=0.50, and nonsphericity correction  $\varepsilon = 1$ , recruitment of 40 individuals with PTSD and 40 trauma-exposed controls will provide greater than 91.9% statistical power to detect this magnitude differential effect size.

MRI

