6. **Subject Population:** Provide a detailed description of the types of human subjects who will be recruited into this study.

We will recruit men and women aged 18-55 who have been exposed to trauma, with and without PTSD into the study. To ensure that we study a representative cohort of both PTSD and trauma-exposed individuals whose symptoms span the full dimensional spectrum, we will use a sampling strategy that is more inclusive than exclusive, and we will recruit subjects who present with a wide range of PTSD symptoms, ranging from unaffected to severely affected trauma survivors. Notably, we will enrich the sample by requiring that 50% meet criteria for a primary PTSD diagnosis. This will allow us to pursue both categorical and dimensional analyses of our study aims. In doing so, the proposed study aligns with both traditional case-control approaches of evaluating the neurobiology of psychiatric disorders, as well as more contemporary approaches, such as the NIMH RDoC project, which embraces a dimensional approach to classifying the neurobiological underpinnings of psychopathology.

7. **Subject classification:** Check off all classifications of subjects that will be specifically recruited for enrollment in the research project. Will subjects who may require additional safeguards or other considerations be enrolled in the study? If so, identify the population of subjects requiring special safeguards and provide a justification for their involvement.

□Children	🗵 Healthy	□Fetal material, placenta, or dead fetus
□Non-English Speaking	Prisoners	Economically disadvantaged persons
Decisionally Impaired	Employees	□Pregnant women and/or fetuses
□Yale Students	Females of childbear	ing potential

NOTE: Is this research proposal designed to enroll children who are wards of the state as potential subjects? Yes □ No ⊠

8. Inclusion/Exclusion Criteria: What are the criteria used to determine subject inclusion or exclusion?

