### Inclusion criteria:

- Men and women, aged 18-55 years, any race, with a history of trauma exposure
- Subjects with posttraumatic stress disorder (PTSD) will have a primary, current diagnosis of PTSD according to DSM-V criteria (i.e., CAPS-5 ascertained diagnosis)
- Trauma-exposed controls will have a CAPS-5 score of 0-22 (no/minimal to mild/subthreshold symptoms)
- Able to read and write English and to provide voluntary, written informed consent

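### CAPS-5 both assigns the two groups and supplies two outcomes of the pooled VT regression, so a pure case-control difference in VT can appear as a severity gradient

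*Combined protocol and SAP*

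**What the plan says.** **Group assignment** (Section I, item 8, Inclusion criteria). Cases need a "primary, current diagnosis of PTSD according to DSM-V criteria (i.e., CAPS-5 ascertained diagnosis"; no minimum score is set for them. For controls: "Trauma-exposed controls will have a CAPS-5 score of 0-22 (no/minimal to mild/subthreshold symptoms".

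**Sampling intent** (item 6, Subject Population). The plan wants "individuals whose symptoms span the full dimensional spectrum", "ranging from unaffected to severely affected trauma survivors", enriched by "requiring that 50% meet criteria for a primary PTSD diagnosis".

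**Baseline regression** (item 13, Statistical Considerations). Global VT is the independent variable, and "clinician interview-based measures of threat and loss symptoms will be modeled as dependent variables". The Sample Size Calculation under item 4 lists five outcomes, ending with "CAPS-5-assessed threat and loss symptoms, global cognition". It tests at a two-sided 0.05/5 = 0.01 on n = 80 and allows as many as ten predictors without naming any. Item 13 enters group and rs6971 in the ANCOVA that precedes this regression, but names neither in the regression.

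**Other analyses in item 13.** The only analysis by PTSD status concerns changes after LPS. The Aim 3 correlations, which choose the markers for the mediation tests, adjust for rs6971 only.

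**Pilot** (item 3, Preliminary studies, d). The correlations of VT with cognition were "adjusted for the rs6971 polymorphism on the TSPO gene and psychiatric disorder".

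**The concern.** Aim 1 makes two claims: VT is higher in PTSD than in trauma-exposed controls, and VT rises with symptom severity. Because CAPS-5 decides group membership, CAPS-5 scores differ strongly between the groups by design. A mean VT difference then produces a positive slope of CAPS-5 on VT in the pooled sample, whether or not VT tracks severity within either group. Without a diagnosis term the second test partly repeats the first, and the dimensional conclusion is not separate evidence. The baseline Aim 3 analyses use the same symptom outcomes and also omit diagnosis.

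Direct selection affects two of the five outcomes. Dot probe, reward task and cognition scores do not decide entry, although pooling can mix between-group and within-group effects there too.

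**Working it through.** **1. The plan's own figures.** Group comparison, d = 0.80 with 40 per group: noncentrality 0.80 × √(40/2) = 3.58 on 78 df gives 94.2%, as stated. Regression: f² = 0.25/0.75 = 0.333 and λ = 80 × 0.333 = 26.7. One coefficient tested at 0.01 gives 99.3%, close to the stated 99.2%; the overall test with 10 numerator df would give 81.2%. So the stated power fits a single slope estimated on all 80 subjects pooled.

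**2. Expected pooled correlation with no within-group relation.** It is roughly the product of two correlations:
- VT with group: d/√(d² + 4), which is 0.80/2.154 = 0.371 at d = 0.80 and 1.02/2.245 = 0.454 at d = 1.02.
- CAPS-5 with group: 0.84-0.93 under the distributions in step 3.

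The products are about 0.31-0.35 and 0.38-0.42. The critical r at two-sided 0.01 on 78 df (t = 2.640) is 2.640/√(78 + 6.97) = 0.286. A pure group difference therefore exceeds the threshold on average.

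**3. Simulation.** 20,000 trials per scenario, 40 + 40 subjects, VT shifted by d in PTSD with unit SD, and zero VT-CAPS-5 slope inside each group. The documents give no CAPS-5 distributions, so these are assumed: controls have mean parameter 8 and SD 7, truncated to 0-22; PTSD is as tabulated, with upper limit 80. Here d is taken as genotype-adjusted. The value d = 0.38 is the plan's figure from 2 versus 2 subjects, used only as a low value.

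Share of trials with pooled p<0.01:

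| PTSD mean, SD, floor | d=0.38 | d=0.80 | d=1.02 |
|---|---|---|---|
| 38, 9, 23 | 14.2% | 71.9% | 92.2% |
| 30, 7, 23 | 14.1% | 70.2% | 91.9% |
| 28, 8, 15 (overlaps controls) | 11.5% | 62.6% | 86.5% |
| 45, 9, 23 | 15.2% | 74.5% | 93.5% |

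At d = 0 the pooled rate is about 1%. With a group term it is 0.9-1.1% in every scenario. In one continuous sample with no gap and a step in VT of 0.80, the pooled rate is still 58%.

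**4. If rs6971 is left out.** Preliminary studies (a) gives a roughly 2-fold VT difference between high and medium binders. The pilot implies a within-genotype CV of 0.215/1.02 = 21%. Take an assumed genotype gap of 3.3 SD and a 50/50 mix. The variance becomes 1 + 3.3²/4 = 3.72, so d = 0.80 shrinks to 0.80/√3.72 = 0.41. VT with group becomes 0.20 and the pooled r about 0.20 × 0.91 = 0.18. Simulation with a 2-fold ratio and 50-65% high binders gives 15-20% at d = 0.80 and 27-34% at d = 1.02. With a 1.5-fold ratio it gives 33-38% and 55-60%.

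**5. Cost of the group term if the gradient is real.** A true linear VT-CAPS-5 relation was simulated across all 80 subjects. Power at 0.01:

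| True pooled r | Pooled | Group-adjusted | PTSD only, n=40 |
|---|---|---|---|
| 0.33 | 70% | 11% | 7% |
| 0.40 | 90% | 18% | 13% |
| 0.47 | 98% | 29% | 20% |

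The partial r falls to 0.15-0.23 because group absorbs much of the CAPS-5 range. An adjusted model would have 57% power at a partial r of 0.30 and 87% at 0.39, but the partial r expected here is smaller.

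**The case against.** The strongest reply is that the pooled slope is the declared target. The plan treats trauma-related symptoms as dimensional and promises both categorical and dimensional analyses. Group is largely a dichotomised CAPS-5, so adjusting a CAPS-5 outcome for it removes real gradient; step 5 shows how much. This stands. It rules out replacing the pooled slope with the adjusted one. It does not make the pooled slope able to tell a gradient from a step between groups.

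Group could also be among the unnamed predictors. That is possible, but nothing commits to it. The same silence covers rs6971, so the high rates in step 3 require genotype to be in the model and diagnosis out of it.

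A reader might infer more than the documents support:
- *That the middle of the CAPS-5 scale is excluded, leaving two separate clusters.* Diagnosed subjects with mid-range scores are eligible; only undiagnosed people above 22 are not. The artefact also persists with overlapping scores and with no gap.
- *That a false gradient is certain.* The rate depends on d, on genotype handling and on CAPS-5 distributions that the documents do not give. The simulation uses a CAPS-5 total, whereas the outcomes are threat and loss subscores whose group separation is unknown.
- *That the pilot adjustment sets a precedent.* It concerned cognitive outcomes in a sample mixing healthy controls, alcohol dependence and PTSD.

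**Conclusion.** The concern holds in a limited form. For the CAPS-5 threat and loss outcomes, the baseline regression as described cannot separate a severity gradient from a case-control difference in VT. If there is only a group difference, the chance of a significant pooled slope at 0.01 is about 63-75% (d = 0.80) or 87-94% (d = 1.02) with rs6971 in the model. It is about 15-20% or 27-34% with rs6971 omitted and a 2-fold genotype gap, and 12-15% at d = 0.38 with adjustment. All of these are well above 1%. They rest on assumed CAPS-5 distributions and a zero within-group relation, and they apply only if diagnosis is not entered. The Aim 3 baseline analyses share the omission, but no rate was computed for mediation. Separately, barring undiagnosed people above 22 does not match the full-spectrum sampling claim in item 6.

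**What to change.** In item 13, for the CAPS-5 threat and loss outcomes of the baseline regression and for the baseline Aim 3 analyses:

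1. Keep the pooled slope. Report beside it the group-adjusted (within-group) slope and the PTSD-only slope, each with a confidence interval and with rs6971 in the model.
2. State in advance that the pooled slope includes the case-control contrast and is not by itself independent evidence of a severity gradient, and that a null within-group slope does not refute one.
3. State the power of the within-group estimates.
4. Align the full-spectrum wording in item 6 with the entry criteria in item 8.

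The cost is a few extra model fits and some wording; recruitment and procedures are unchanged. The downside is low power for the within-group estimates: about 10-29% at 0.01 if the true pooled r is 0.33-0.47. They are best read through their intervals.
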